### **Testing for Count Fingers Vision, Hand Motion Vision and Light Perception/No Light Perception (NLP) Vision**

If the subject’s visual acuity is so poor that he/she cannot read any chart letters when tested at one meter then the subject’s ability to count fingers, detect hand motion, or have light perception should be evaluated.

### **Testing for Count Fingers Vision**

In testing for count fingers vision, the examiner's hand holding 1, 2, or 5 fingers is held steady at a distance of two feet directly in front of the eye being examined. The FE is completely occluded with a patch on the face. A light should be shown directly on the hand from behind the subject. The examiner's fingers should be presented in random order and repeated 5 times. Eccentric fixation, if present, should be encouraged. If the subject correctly identifies three of the five presentations, then count fingers vision is noted. If not, then the subject must be tested for hand motion vision.

### **Testing for Hand Motion Vision**

The examiner's hand with all fingers spread out should be extended two feet directly in front of the eye being examined. The FE should be occluded with a patch on the subject's face. A light should be shone directly on the hand from behind the subject. The examiner's hand should be moved in an up-and-down direction (vertically) or in a side-to-side direction (horizontally) at a constant speed of approximately one back and forth presentation per second. The subject is instructed that the examiner's hand will be presented and they will have to respond to the question: "What am I doing with my hand?" This should be repeated five times. Three out of five correct responses indicate that hand motion vision is present. If the subject does not correctly identify three of five presentations, then you must test for light perception.

### **Testing for Light Perception/NLP Vision**

Light perception should be tested with an indirect ophthalmoscope in a darkened room. The indirect ophthalmoscope light should be in focus at 1 meter with the rheostat set at maximum voltage. From that distance the beam should be directed in and out of the eye at least four times, and the subject should be asked to respond when he or she sees the light. If the examiner is convinced that the subject perceives the light, vision should be recorded as "light perception", if not, vision should be recorded as "no light perception (NLP)".

### 17.3.10 Refraction Sequence Chart

Refraction Protocol Summary							
Vision with Best Correction (Refraction Distance)	Sphere		Cylinder			Sphere Refinement	
	Power (a)	Increment	Axis (b)	Power (c)	Increment	Power (d)	Increment
20/10 - 20/80 (4 meters)	+ .50	+ .50	.25	.25	+ .25	+ .25	+ .25
	- .50	- .50	JCC	JCC	- .25	- .25	- .25
20/100 - 20/160 (4 meters)	+1.00	+1.00	.50	.50	+ .50	+ .50	+ .50
	-1.00	-1.00	JCC	JCC	- .50	- .50	- .50
20/200 - 20/400 (1 meter)	+2.00	+2.00	1.00	1.00	+1.00	+1.00	+1.00
	-2.00	-2.00	JCC	JCC	-1.00	-1.00	-1.00
<20/400 (1.0 meters)	+2.00	+2.00	No cylinder test			No refinement	
	-2.00	-2.00					

Sequence of Refraction: (a) - (d)

## 17.4 Intravitreal Administration Protocol

This protocol applies to avacincaptad pegol and Sham injections.

**The injection volume for avacincaptad pegol 2 mg/eye is 0.10 mL (100 µL).**

The avacincaptad pegol and Sham injections must be performed by the unmasked ophthalmologist at the clinical site.

Subjects will receive one or two intravitreal injections (including Sham) at each monthly visit. Subjects will receive one of the following treatments at each injection visit:

- Avacincaptad pegol 2 mg/eye
- Avacincaptad pegol 4 mg/eye (administered as two injections of avacincaptad pegol 2 mg)
- Sham
- Sham + Sham

**Only an ophthalmologist who is experienced with intravitreal injections may perform the intravitreal injections.**

**When there are two intravitreal injections to be administered on the same day, this intravitreal preparation and administration procedure MUST be followed for both injections, i.e., subjects MUST undergo a second preparation procedure and povidone-iodine (Betadine®) application prior to the second injection.**

In addition to the procedures outlined, any additional safety measures in adherence to specific institutional policies associated with intravitreal injections may be utilized.

NOTE: Prior to the intravitreal injection, direct ocular massage using a sterile cotton-tip applicator at the intended site of injection may be utilized at the Investigator's discretion. However, a paracentesis **MAY NOT** be performed **prior** to injection of the intravitreal drug.

NOTE: Pre-operative antibiotic drops are NOT required prior to the scheduled injection(s) of intravitreal drug. In addition, peri-operative and post-operative antibiotic drops are NOT required at the time of the procedure or after the procedure, respectively. However, if it is considered the standard of care at the individual

institution, appropriate broad spectrum topical antibiotics (topical ofloxacin, levofloxacin, or an antibiotic drop with comparable antimicrobial coverage) may be prescribed for subject use at the discretion of the investigator.

**NOTE: Intravitreal administration of avacincaptad pegol is contraindicated if active inflammation and/or suspected or active ocular or peri-ocular infection is present.**

**NOTE: Clinically significant blepharitis should be treated and resolved prior to randomization.**

### **Before the Injection Day**

- 1) If pre-operative topical ofloxacin, levofloxacin, or an antibiotic drop with comparable antimicrobial coverage therapy is ordered by the investigator, the subject should be instructed to initiate the use of such antibiotic drops according to the regimen selected at the discretion of the investigator. The antibiotic drops should be provided to the subject with clear instructions of how to use them at the visit immediately prior to each planned injection.

### **Preparation on the Day of the Injection**

- 2) Approximately one hour prior to injection, topical 1% tropicamide (e.g., Mydracyl) and 2.5% phenylephrine (e.g., Neo-Synephrine) from new bottles should be applied topically to achieve adequate pupillary dilation. If 2.5% phenylephrine is not available, another dilating drop may be used at the discretion of the investigator.
- 3) Injection preparation (for the following, new povidone-iodine bottles must be used and cannot be shared between subjects):
  - a. Apply single use topical anesthetic drop(s) to the eye.
  - b. Apply 2-3 drops of povidone-iodine to the injection site.
  - c. OPTIONAL: Apply 2-3 drops of povidone-iodine to the lower fornix and/or use sterile cotton-tipped applicators soaked in 5% or 10% povidone-iodine to swab the upper and lower eyelid margins and the upper and lower eyelashes.
- 4) Place a sterile eyelid speculum to stabilize the eyelids.

- 5) Consider additional anesthesia with the application of one or two cotton-tipped applicators soaked in topical anesthetic over the intended injection site for at least 30 seconds. Subconjunctival anesthesia (0.5 mL of 2% xylocaine without epinephrine subconjunctivally at the intended injection site) can be used if the investigator believes that topical anesthetic is not sufficient to minimize discomfort. Lidocaine gel is not recommended.
- 6) Encourage the study participant to look superonasally (if injection site is inferotemporal) during the application of the povidone-iodine. Apply one of the following to the conjunctiva directly over and surrounding the intended injection site:
  - a. A cotton-tipped applicator soaked in 5% or 10% povidone-iodine.
  - b. A 10% povidone-iodine swabstick.
  - c. At least 1-3 drops of 5% povidone-iodine (at least enough to cover the intended injection site).
- 7) Allow 30-60 seconds for the povidone-iodine to be in contact with the injection site before injection.

NOTE: As indicated above, injection preparation must include the use of povidone-iodine either applied directly to the injection site using topical drops, a cotton-tipped applicator, or a swabstick. If a study participant experiences an adverse reaction to povidone-iodine, other approaches to limit the exposure of povidone-iodine may be permitted. However, **a study participant may not receive a study intravitreal injection without use of povidone-iodine directly to the injection site just prior to the injection.**

- 8) Sterilized calipers should be used to measure the injection site. The entry site of the needle for the intravitreal injection should be 3.0-3.5 mm from the limbus in aphakic/pseudophakic subjects, and 3.5-4.0 mm in phakic subjects.

**NOTE: During the preparation and injection of the drug, investigators, ancillary staff and subjects should refrain from talking. If talking becomes absolutely necessary, the investigator**

should face away from the bare needle and the injection site to avoid contamination of the needle and injection site. Wearing a mask during the preparation and injection of the drug is optional.

**1st Injection (avacincaptad pegol 2 mg/eye or Sham)**

**If the Subject is Randomized to Receive avacincaptad pegol 2mg (0.10 mL injection volume):**

- a. Use sterile gloves during preparation and administration of the injectable drug.
- b. Using aseptic technique, 0.2 mL of the avacincaptad pegol injection vial contents are withdrawn through a 5-micron 19-gauge filter needle attached to a 1-mL sterile syringe (supplied). Care should be taken to aim the filter needle toward the center of the vial. The filter needle should be discarded after withdrawal of the vial contents and should not be used for intravitreal injection. The filter needle should be replaced with the sterile 30-gauge needle (supplied) for the intravitreal injection. The contents and any air bubbles should be expelled until the plunger tip is aligned with the line that **marks 0.10 mL on the syringe for avacincaptad pegol 2mg.**
- c. Insert the drug into the vitreous cavity pointing toward the optic nerve via the pars plana. Once the needle is in place, continuous pressure should be applied to the syringe for approximately 10 seconds to assure slow, even delivery of all drug.
- d. As the needle is withdrawn, a sterile cotton tip applicator should be rolled over the entry site to minimize the risk of drug reflux. This should be held in place for a full 10 seconds.
- e. The eye can then be irrigated as per the typical practice pattern of the investigator to minimize irritation from the aseptic procedure.
- f. Two drops of single use antibiotic may be placed over the injection site at the end of the injection procedure at the discretion of the investigator. This same antibiotic may then be used four times daily for 3 days following the injection at the discretion of the investigator.

- g. One to two minutes following the intravitreal injection, subjects should be examined with indirect ophthalmoscopy to assure that the optic nerve is perfused, the retina is attached and there is no new intraocular hemorrhage.
- h. **If a second injection is to be administered, the second injection may NOT be administered until the IOP is  $\leq 21$  mmHg or within 5 mmHg of the baseline IOP on the day of injection.** If the IOP is **not**  $\leq 21$  mmHg or within 5 mmHg of the baseline IOP, the IOP should continue to be monitored until it is  $\leq 21$  mmHg or within 5 mmHg of the baseline IOP (record IOP at this time) before proceeding to the second injection.
- i. If there is no second injection, the IOP should be measured and recorded 30 minutes after the intravitreal injection is administered. Monitor the IOP until it is below 30 mmHg; the subject should not be discharged until at least 30 minutes after the 1st injection and the IOP is below 30 mmHg or at a lower level as determined by the investigator.

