FORMULATION AND PRESENTATION:	
Formulation
 
Avacincaptad pegol is formulated at a concentration of 20 mg/mL (oligonucleotide mass) in 10 mM phosphate buffered saline at pH 6.8-7.8 as a sterile aqueous solution. The drug product is preservative-free and intended for intravitreal injection only. The drug product should not be used if cloudy or if particles are present.
 
Presentation
 
The clinical supply kits contain either an avacincaptad pegol standard 2R vial [Schott] or an empty 2R vial, along with BD syringe and BD filter needle.
 
The drug product was originally presented in a USP Type I high recovery glass vial that contained a 0.5 mL v-shaped well sealed with FluoroTec®-coated, halobutyl rubber stoppers and red aluminum crimp seals. In March 2023, the drug product was transitioned to presentation in a 2 mL (ISO 2R) Type I glass vial, stoppered with FluoroTec-coated, halobutyl rubber stopper, and sealed with aluminum crimp seals.
 
Instructions for Use (IFU) are provided directly to the study site.
 
Dosing Information
 
The avacincaptad pegol 2 mg/eye dose will be administered in a total injection volume of 0.1 mL (100 <math>\mu</math>L). Avacincaptad pegol 4 mg/eye will be administered as two 0.1 mL (100 <math>\mu</math>L) injections.
 
Comparator Sham Procedure
 
To preserve the randomized treatment arm masking, subjects will have the sham procedure performed at study treatment visits.

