### 10.2 Trial Assessments

The following dosing days apply to the Induction Phase.

D0	D0 = The first day of dosing at each monthly timepoint.
D14	D14 = The second day of dosing, 14 days after D0.

The following evaluations, as outlined in the Study Assessments Chart (Section 3) will be performed on the days specified below:

*Note:*

- ***Concomitant medications should be assessed at every study visit.***
- ***Adverse events should be assessed starting at Day 1 after the first dose of trial drug.***

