**If the Subject is Randomized to Receive Sham:**

- a. Use sterile gloves during preparation of the empty syringe and during the simulated injection.
- b. Use the sterile empty syringe **without** an attached needle.
- c. Use the blunt opening of the syringe barrel to indent the conjunctiva in the inferotemporal quadrant to simulate the pressure on the eyeball of an injection.

***Note: This procedure should be performed in a manner so that the subject is not aware that the syringe has no needle, and that the globe is not being penetrated (i.e. the subject should be instructed to look away).***

- d. The eye can then be irrigated as per the typical practice pattern of the investigator to minimize irritation from the aseptic procedure.
- e. One to two minutes following the Sham injection, subjects should be examined with indirect ophthalmoscopy to assure that the optic nerve is perfused, the retina is attached and there is no new intraocular hemorrhage.
- f. **If a second injection is to be administered, the second injection may NOT be administered until the IOP is  $\leq 21$  mmHg or within 5 mmHg of the**

**Baseline IOP on the day of injection.** If the IOP is **not**  $\leq 21$  mmHg or within 5 mmHg of the baseline IOP, the IOP should continue to be monitored until it is  $\leq 21$  mmHg or within 5 mmHg of the baseline IOP (record IOP at this time) before proceeding to the second injection.

- g. If there is no second injection, the IOP should be measured and recorded 30 minutes after the intravitreal injection is administered. Monitor the IOP until it is below 30 mmHg; the subject should not be discharged until at least 30 minutes after the 1st injection and the IOP is below 30 mmHg or at a lower level as determined by the investigator.

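### The active and Sham step lists in Protocol Appendix 17.4 differ in two steps a participant can perceive (the cotton-tip hold and the optional antibiotic drops), an avoidable masking risk

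*Protocol*

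**What the plan says.** The Protocol synopsis, under the comparator procedure, states the purpose of the Sham: "To preserve the randomized treatment arm masking, subjects will have the sham procedure performed at study treatment visits". Appendix 17.4 applies to both treatments. Its preparation steps are common to both arms, but the injection itself is described in arm-specific lists, once for the first injection and again for the second.

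The active lists say, at step d: "As the needle is withdrawn, a sterile cotton tip applicator should be rolled over the entry site to minimize the risk of drug reflux". The next sentence adds: "This should be held in place for a full 10 seconds". Step f says: "Two drops of single use antibiotic may be placed over the injection site at the end of the injection procedure", at the investigator's discretion, and continues: "This same antibiotic may then be used four times daily for 3 days following the injection at the discretion of the investigator".

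The Sham lists describe the simulated injection as follows: "Use the blunt opening of the syringe barrel to indent the conjunctiva in the inferotemporal quadrant to simulate the pressure on the eyeball". They then go to optional irrigation and to ophthalmoscopy. Their masking note concerns hiding the missing needle and the fact that the eye is not entered.

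A general note near the start of Appendix 17.4 says that antibiotic drops are not required before, during or after the procedure. It lets the investigator prescribe them where that is the institution's standard of care, and it does not mention arm. Section 10.2 of the Protocol says: "Concomitant medications should be assessed at every study visit".

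**The concern.** The lists are what the unmasked injector works from, and that person knows that a Sham eye has not been entered. An injector can follow them to the letter and hold a cotton tip to the eye, and give drops, in one arm only. The participant can feel the hold and certainly knows about drops taken at home. Those drops can then be recorded at the next medication review, where masked staff may learn of them.

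BCVA and microperimetry depend on what the participant does during the test. They stand second and third in the fixed testing sequence of SAP Section 2.1. Under Protocol Section 11.4.2 the masked assessor judges how every adverse event relates to study drug. If participants or that assessor come to suspect the arm, these outcomes are the ones that could shift. Neither document plans a check of whether masking held.

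**Working it through.** There is no plan figure to reproduce, so the check is a comparison of the lists (letters are the list steps).

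| Element | Active, 1st injection | Active, 2nd injection | Sham, 1st | Sham, 2nd |
|---|---|---|---|---|
| Injection or simulation | c | c | c | c |
| Cotton-tip hold, 10 seconds | d | d | absent | absent |
| Optional irrigation | e | e | d | d |
| Optional antibiotic drops, optional 3-day course | f | f | absent | absent |
| Indirect ophthalmoscopy | g | g | e | e |
| IOP monitoring | h, i | h | f, g | f |

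After the injection or its simulation, two elements appear in one arm's lists only.

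Next, whether common text fills the gap:

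- The general note allows post-injection antibiotics in either arm but does not ask for equal use, and it does not address the cotton tip.
- The section on the days before injection handles pre-operative antibiotics for both arms, so the appendix does have common antibiotic text. The post-injection step was not placed there.
- The closing section that covers all injections, Sham included, repeats ophthalmoscopy, IOP and discharge advice. It mentions neither the cotton-tip hold nor post-injection antibiotics.

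Then, who can notice what:

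- Participant: both elements.
- Masked staff: not the procedure. Section 11.4.2 keeps them away from the breaking of the kit seal until the injections are finished and the components disposed of, and the unmasked injector does the post-injection examination and tonometry. They can learn only of take-home drops, through the medication review.
- Visual acuity examiners: Appendix 17.3 denies them the participant's chart, so the medication record should not reach them that way.

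Scale, from Protocol Section 9.2.3 (6 doses of 2 mg, each one injection; 15 doses of 4 mg, each two injections; Sham follows the same visits):

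- Dosing days: 6 + 15 = 21.
- Procedures: 6 × 1 + 15 × 2 = 36.
- Days on drops in the active arm, if a 3-day course followed every dosing day: 21 × 3 = 63 at most.
- Difference between arms in days on drops: from 0 (no use, or equal use) to 63 (every course in the active arm, none in Sham). Both ends are assumptions about site practice; the documents do not say what sites did.

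**The case against.** The strongest reply is that antibiotics are not reserved for the active arm. Step f is optional, the general note covers both arms, and Protocol Section 11.4 makes the principal investigator responsible for keeping the participant, the adverse event assessor and the visual acuity examiner masked. Handing out drops by arm would sit badly with that duty. If drops are not used, or are used equally, that difference is zero. In a parallel-arm trial each participant also sees only one procedure, so a 10-second hold or a course of drops reveals the arm only to someone who knows what the other arm receives. All of this stands. It limits the point to a risk, but it does not remove the inconsistency: nothing in Appendix 17.4 tells the injector to treat the arms alike, and the optional drops do not explain the missing cotton-tip step.

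Several stronger readings are tempting and are not supported:

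- A reader might infer that masked staff can see the difference. Section 11.4.2 rules that out for the procedure itself.
- A reader might count the roughly 10 seconds of steady pressure in active step c as a third difference. That pressure is on the syringe, to deliver the drug slowly; the text does not describe 10 seconds of pressure on the eye, and Sham step c is meant to imitate the pressure of an injection.
- A reader might put a bias in letters on BCVA. That needs a rate of correct guessing and a letter shift per guess, and the documents give neither.
- A reader might want an analysis without the sites that used drops unequally. That selects on behaviour after randomization in a trial of about 120 participants. It is a debatable trade-off and is not asked for here.

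**Conclusion.** The two sets of lists differ, for both injections, in the cotton-tip hold and the optional antibiotic step, and no common text closes the gap. Followed as written, the arms can differ in what participants experience at up to 36 procedures over 21 dosing days, and in what is recorded as concomitant medication. A reader might conclude that masking has failed or is undermined; the documents do not show that. They show an avoidable risk whose actual size depends on site practice and on what participants know of the other arm, and neither is documented.

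The exposure is mainly in BCVA and microperimetry. It extends to the masked assessor's causality judgement only through take-home drops. The primary endpoint is measured on images analyzed by an independent reading center and is little exposed. BCVA is formally tested only if the primary endpoint is significant, which further limits the confirmatory consequences.

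**What to change.** In Protocol Appendix 17.4, reconcile the general antibiotic note, the two active lists and the two Sham lists, so that the steps a participant can perceive and the post-injection medication that is recorded do not depend on arm. No view is taken on whether antibiotics should be used or on how the procedure should be done.

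In the SAP, before unmasking, add one table of post-injection topical antibiotic use in the study eye by arm and site. SAP Section 4.2.4 already summarizes concomitant medications by treatment group, by therapeutic and chemical subgroup and preferred name. The addition is the restriction to this use and the split by site, which would show whether the risk materialized. It assumes that the medication record identifies the treated eye and the timing, which the documents do not state.

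The cost is appendix wording, a few seconds more per Sham procedure, and one table from data already collected. SAP Appendix 1 describes allocation in the past tense, so the wording change may come too late for some or all injections in this trial; the table keeps its value either way.

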SYNOPSIS	
	
(ONL) measured by a horizontal scan through the foveal center using SD-OCT from Baseline through Month 18.
 
 
• Time to persistent vision loss (defined as BCVA loss <math>\geq</math> 10, 15 or 20 letters from Baseline at two or more consecutive visits through Month 18).
 
• Emergence of at least one new atrophic lesion (DDAF) measured by FAF through Month 18.
 
 
Safety Endpoints:
 
 
• Adverse events, vital signs, ophthalmic variables [ophthalmic examination, intraocular pressure (IOP), fluorescein angiogram (FA), FAF, SD-OCT, microperimetry], ECG and laboratory variables.
 

PLANNED SAMPLE SIZE:	Approximately 120 subjects will be enrolled in this study, 60 per dose group.
SUBJECT SELECTION:	Subjects of either gender, aged 18 – 60 years of age (inclusive), with the diagnosis of STGD1.
TEST DRUG DOSAGE:	Subjects randomized to avacincaptad pegol will receive 6 doses of avacincaptad pegol 2 mg and 15 doses of avacincaptad pegol 4 mg.

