### 7.2 Tonometry

Tonometry will be performed at all timepoints specified Section 10.2 “Trial Assessments”. On days when two injections are given, the second injection may not be administered until the IOP is  $\leq 21$  mmHg or within 5 mmHg of the pre-injection IOP, at which time the IOP is recorded. After the second injection and also on days with only one injection, tonometry must be performed at least 30 minutes after the injection and IOP must return to  $< 30$  mmHg before the subject leaves the clinic. For the post-injection tonometry, proper care should be taken to minimize the risk of contamination.

Goldmann applanation tonometry must be performed at Screening, Pre-Injection (Day 1, Month 6, Month 9, Month 18) and Early Withdrawal. Tono-Pen tonometry may be used at all other timepoints, but Goldmann applanation tonometry must be used to verify IOP for a post-injection reading of  $\geq 30$  mmHg occurring more than 30 minutes post-injection, or for a reading of  $\geq 30$  mmHg at any other time.

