#### **After All Injections (including Sham injections)**

- 1) One to two minutes following each intravitreal injection, subjects should be examined by ophthalmoscopy to verify reperfusion of the central retinal artery in the immediate post-injection period. Verify that the retina is attached and that there is no new intraocular hemorrhage.
- 2) After each intravitreal injection (including Sham), check the intraocular pressure (IOP) while maintaining a clean field.
  - a. If a second injection is to be administered, monitor the IOP after the 1st injection until it is **≤ 21 mm Hg or within 5 mm Hg of the baseline IOP on the day of injection**; record the IOP at this time.

- b. The IOP should be measured and recorded 30 minutes after the last injection (whether it is the first or second injection). Monitor the IOP until it is below 30 mmHg; the subject should not be discharged until at least 30 minutes after the 2nd injection and the IOP is below 30 mmHg or at a lower level as determined by the investigator.
  - c. If a Tono-Pen is used to check pressure, a clean Tono-Pen condom should be placed on the tip before taking each measurement. If applanation tonometry is used, the applanator tip should be swabbed with alcohol and let to dry before using it to measure IOP. Sterile fluorescein strips and single use proparacaine bottles should be used for all subjects. "Fluoracaine" or other combination fluorescein sodium and proparacaine HCl mixtures should only be used if single use presentation is available, and then only if single use bottles are available. Intraocular pressure may be lowered by pharmaceutical or surgical intervention, if required. Treatment should be initiated whenever IOP is increased to the extent that the central retinal artery remains closed and the subject has NLP for more than 1-2 minutes or as per investigator judgment. Transient graying or obscuration of vision following injection, however, is expected and should not be treated. See below for additional information concerning paracentesis.

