1.3 Randomization

Participants will be randomized in a 1:1 ratio to the following two treatment groups: ACP and Sham.

Participants will be centrally allocated to one of the two treatment groups by a dynamic minimization procedure (see Section 5.1 Appendix 1 for details). Randomization will be stratified by site and performed using an IRT system based on the stratification information to randomize each participant and assign a treatment group. Details of the randomization procedure can be found in Appendix 1.

All participants will be treated as follows:

Induction Phase: Administered starting on Day 1, 14 days apart for a total of 6 administrations (Day 1 – Month 2):

- ACP 2mg/eye or Sham

Maintenance Phase: Administered monthly (Month 3 – Month 17):

- ACP group continued with ACP 4 mg/eye (administered as two injections of ACP 2 mg)
- Sham group continued with Sham + Sham to maintain the masking

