4.6.5.1.2 Intraocular Pressure

IOP will be summarized by treatment group and visit, including all pre-injection, “IOP after first injection”, and “IOP after second injection” measurements for applicable visits. An additional tabular summary of the percentage of participants in categories of IOP will be presented by treatment group, visit, and injection time (pre-injection, IOP after first injection, IOP after second injection). Baseline IOP for the study eye will be taken as the average of the last two pre-treatment values, this will typically be the Screening and Day 1(D0) pre--injection values. If there is only one pre-treatment value present, then this will be the baseline value. Baseline IOP for the fellow eye will be the last pre-treatment value, this will typically be the value at Screening.

“IOP after injection” is defined as the IOP measurement that is closest in time to the protocol-specified post-injection timepoint (but at least 30 minutes post-injection). If there are two closest measurements equidistant to this timepoint, then the measurement after the protocol-specified timepoint will be used.

Mean IOP over time of all scheduled measurements (pre-injection, IOP after first injection, and IOP after second injection, etc.) will be plotted by treatment group.

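### On two-injection days the IOP recorded after the first injection is capped by the release threshold, and the SAP's definition of that value does not match how the protocol collects it

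*Protocol*

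**What the plan says.** **Number of visits.** Protocol Section 2 states: "Subjects randomized to avacincaptad pegol will receive 6 doses of avacincaptad pegol 2 mg and 15 doses of avacincaptad pegol 4 mg". Each 4 mg dose is two injections. SAP 1.3 gives the same span for both arms, with the sham arm receiving two sham procedures.

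**What is recorded after the first of two injections.** Four places agree.
- Protocol 7.2 bars the second injection until IOP is at most 21 mmHg or within 5 mmHg of the pre-injection value, "at which time the IOP is recorded".
- Protocol 17.4, 1st Injection, active arm, step h: monitoring continues until IOP is at or below 21 mmHg or "within 5 mmHg of the baseline IOP (record IOP at this time) before proceeding to the second injection".
- The sham arm, step f, uses the same rule.
- Protocol 17.4, After All Injections, item 2a, repeats it: "record the IOP at this time".

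Item 2c adds: "Intraocular pressure may be lowered by pharmaceutical or surgical intervention, if required". None of these passages requires the readings before release to be recorded, and none forbids it.

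**What is recorded after the last injection.** Item 2b sets a clock time and no threshold for recording: "The IOP should be measured and recorded 30 minutes after the last injection (whether it is the first or second injection").

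**What the SAP does with the values.** SAP 4.6.5.1.2 summarises IOP by arm and visit before injection, after the first and after the second, and plots the means. It continues: "An additional tabular summary of the percentage of participants in categories of IOP will be presented by treatment group, visit, and injection time". It defines the post-injection value as the reading nearest the protocol's post-injection timepoint, provided that at least 30 minutes have passed since injection.

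**The concern.** The required value is selected for having met the release condition, possibly after waiting or after IOP-lowering treatment. The output nevertheless carries a label that reads as the pressure response to the first injection. Sham involves no needle and no injected volume, so the difference between arms at this timepoint is where an effect of the first 0.1 mL would be expected to show. If both arms are held under the same ceiling, the table and plot can look similar whatever that effect is. IOP is a named safety variable, and a reader of the study report would have no notice of the truncation.

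There is a second mismatch. The protocol gives the release reading no clock time, while the SAP accepts only readings at least 30 minutes after injection. Which value enters the cell is therefore not settled by the two documents together.

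**Working it through.** **Count.** Months 3 to 17 inclusive: 17 − 3 + 1 = 15, which reproduces the protocol's 15 doses of 4 mg. With the 6 single-injection visits there are 21 dosing visits, and 15/21 = 71%. At the planned 60 per arm and full attendance, 15 × 60 = 900 first-injection readings per arm fall under the rule.

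**Ceiling.** Let P be that day's pre-injection IOP and R the recorded release reading. Release needs R ≤ 21 or R ≤ P + 5, so

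R ≤ max(21, P + 5), and the largest recordable rise is max(21 − P, 5).

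| P (mmHg) | Ceiling for R | Largest recordable rise |
|---|---|---|
| 8 | 21 | 13 |
| 10 | 21 | 11 |
| 12 | 21 | 9 |
| 14 | 21 | 7 |
| 15 | 21 | 6 |
| 16 | 21 | 5 |
| 18 | 23 | 5 |
| 21 | 26 | 5 |
| 24 | 29 | 5 |

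The largest recordable rise is never below 5 mmHg. For R ≥ 30, P + 5 must be at least 30, so P ≥ 25. Entry requires study-eye IOP of at most 21 mmHg (Protocol 8.2.7). That limit does not bind later visits, so P ≥ 25 is possible but would be unusual. The SAP names no cut points for its IOP categories; 30 mmHg is used here because the protocol uses it for verification and discharge.

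**Illustration of the compression.** The documents give no distribution of first readings, so these inputs are assumptions: P with mean 15 and SD 2.5 or 3, limited to 6–21; first reading equal to P plus a rise with SD 5; recorded value the lower of the first reading and the ceiling; 200,000 draws per case. Ranges span the two SDs.

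| True mean rise | Recorded mean rise, at most | First readings ≥ 30 | Recorded ≥ 30 |
|---|---|---|---|
| 5 | 3.6 | 3.5–4.1% | 0% |
| 10 | 5.7–5.9 | 18.5–19.3% | 0% |
| 20 | 6.6–6.8 | 80–81% | 0% |
| 30 | 6.6–6.8 | over 99% | 0% |

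The 0% column follows directly from limiting P to 21. The informative column is the second: rises of 20 and 30 mmHg become indistinguishable.

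**The 30-minute condition.** Let the release reading fall t minutes after the first injection, and the second injection s minutes after it, with s ≥ t. The final reading is taken at least s + 30 minutes after the first injection.
- If t ≥ 30, the release reading qualifies under SAP 4.6.5.1.2.
- If t < 30, it does not. The final reading does meet the time condition relative to the first injection. The SAP does not say that a first-injection reading must precede the second injection.

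The cell then holds either nothing or a value that belongs to the second injection.

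**The case against.** Several points on the other side are sound.

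- **Smaller rises are visible.** A reader might infer that these tables can show no rise at all. That is not so: 12 to 21 mmHg passes the rule, and if the first check already meets the threshold, the recorded value is the uncensored first reading.
- **Other outputs exist.** A reader might also infer that a large rise would appear nowhere. Protocol 12.1 makes a finding reportable if it brings symptoms, needs intervention or changes dosing, or if the investigator or sponsor judges it an AE. SAP Appendix 2 counts increased IOP as an ocular AE, SAP 4.6.1 tabulates ocular AEs, and its listings give onset relative to the first and second injection. What can escape is a symptomless, untreated rise that settles with waiting and is not judged an AE.
- **One timepoint only.** The same 15 visits have a reading 30 minutes after the last injection, recorded without a threshold condition, as do the six single-injection visits. If the second injection is not given, the 30-minute rule applies to the first. These readings do not replace the missing one: they come later, and at two-injection visits they follow a return to the release level.
- **Interventions are partly captured.** Paracentesis IOPs go on the CRF, and the protocol bars paracentesis before an intravitreal injection, so it is doubtful that one would precede the release reading. IOP-lowering drugs should appear as concomitant medication or AE treatment.
- **Extra readings may exist.** The CRF is not among the documents, and sites may have kept earlier readings. Nothing requires it.

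These points narrow the gap. None of them removes the ceiling on the required value or the mismatch with the SAP definition.

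**Conclusion.** The point holds in limited form. At the 15 two-injection visits, the only post-first-injection IOP that must be recorded is bounded by max(21, pre-injection + 5) mmHg in both arms, and the SAP presents it without saying so. This bound is arithmetic from the stated rule and needs no assumption beyond sites recording what the protocol asks for. The simulated figures are illustrations only. The SAP's 30-minute condition can also leave the cell empty or fill it from the wrong injection; how often depends on the release times, which the documents do not give.

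The documents do not support the wider conclusion that the IOP effect of treatment cannot be assessed at 15 of 21 visits. The defect is confined to one timepoint of a descriptive safety summary and touches no hypothesis test. It should still be corrected before unmasking, because the summary as labelled would look reassuring by construction.

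**What to change.** 1. **SAP 4.6.5.1.2, definition.** For first-injection readings at visits where two injections are given, drop the 30-minute condition and admit only readings taken before the second injection. Keep the present definition for readings after the last injection.
2. **SAP 4.6.5.1.2, label.** Call the threshold value 'IOP at release for second injection' in tables and plot, and state its ceiling of max(21, pre-injection + 5) mmHg in a footnote.
3. **Protocol 7.2 and 17.4, and the CRF.** Record the first IOP reading already taken after the first injection, with its clock time. Tabulate it separately by arm where it exists in source. Where it does not, present only the release-labelled values.
4. **Optional.** Count participants per arm given an IOP-lowering intervention, from the concomitant medication, AE and paracentesis data already collected.

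The release threshold itself is not touched. The cost is one extra CRF value and time for a reading already made, a revised definition and a relabelled output. For visits already completed, only items 1 and 2 may be possible.
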